6.3.3 Concomitant treatments and interventions permitted and prohibited during the study

The use of concomitant medications by any route of administration will not be permitted during the intervention period, except for those specified for the study procedures. The objective of this restriction is to avoid drug interactions that could alter the results of the evaluated variables.

6.3.4 Treatment management

The interventions will be provided by Laboratorios Sophia , SA de CV, for the research center. They will be labeled, reconciled, and weighed beforehand. Treatment management will be the responsibility of the researcher or a designated member of their team.

6.3.4.1 Delivery and receipt

Delivery will be made in sealed cardboard boxes by courier or directly by sponsor staff to the research center's address, according to the study plan.

Reception will be handled exclusively by the research center team, including the researcher. They must verify the condition of the primary packaging (the box). If it shows alterations or defects in its integrity that, in their opinion, could have damaged the contents, they must report this to the sponsor. If the package shows no significant defects, they will open it.

Inside, you must locate the receipt acknowledgment document and the temperature and humidity *data logger* . You must verify that the recorded temperature and humidity comply with the specifications for transport and storage (see section 6.3.4.2 Storage). You will verify the content (interventions) with what is reported in the document. If the document corresponds to the content, you will sign the receipt and send it to the sponsor. If not, you will notify the sponsor.

At the study center, staff assigned by the PI will administer the appropriate treatment to admitted subjects, sufficient for the study period. This treatment will be administered at the baseline visit. The center must record the medication administered.

6.3.4.2 Storage

The medication must be stored in a secure area with restricted access.

Storage temperature should be at room temperature, no more than 30º Celsius.

The research center is required to record the temperature and humidity recorded in the *data logger* , *using the format designated by the sponsor* . This record must include the current temperature and humidity, as well as the minimum and maximum values for each. This must be done at least once a day on weekdays.

These data will be compared by the clinical monitor according to the record in the *data logger* .

6.3.4.3 Return

Research subjects will return their medications to the staff designated by the PI at the center during the final visit. The return will be made by the research center upon the sponsor's instructions. Prior to return, the research center must conduct a count of the assigned medication and the remaining medication to create an inventory that will be used to complete the final medication return form.

6.4 Outcome variables

6.4.1.1 Primary outcome variables

- Security
 - Presence of adverse events.
- Tolerability
 - Eye comfort index

6.4.1.2 Secondary outcome variables

- Tear film break-up time
- Vital signs: HR, RR, SBP.
- Posterior segment
- Quality questionnaire
- Intraocular pressure.
- Visual capacity.
- Laboratory tests: BHc , QS and PFH.
- Ocular surface stains.

6.4.3 Methods and scales to be used for measuring the variables

Variable	Unit	Symbol	Guy	Measurement method	Normal value
Age	Years	--	Continued	Calculation from the date of birth	NA
Gender	Female / Male	F / M	Nominal	Direct questioning	NA
Adverse events	Number of cases	n	Discreet	Counting	NA
Intraocular pressure	Millimeters of mercury	mmHg	Continued	Goldman applanation tonometry	11 - 21

Variable	Unit	Symbol	Guy	Measurement method	Normal value
Visual capacity	Fraction	Snellen	Nominal	Primer	20/20
Tear break-up time	Seconds	s	Continued	Direct count	> 10
Eye comfort index	Points	--	Discreet	Questionnaire	NA
Adverse events	Present / Absent	--	Nominal	Comprehensive assessment	Absent
Vital signs					
Heart rate	Beats per minute	bpm	Discreet	Auscultation	60 – 100
Respiratory rate	Breaths per minute	rpm	Discreet	Auscultation	12 – 24
Systemic blood pressure	Millimeters of mercury	mmHg	Continued	Non-invasive auscultatory measurement	< 120 / 80
Anterior segment					
Ocular surface stains	Degrees	--	Discreet	Direct observation with fluorescein and lissamine green staining	Oxford Scale
Ophthalmological signs and symptoms					
Blood count¹					
Erythrocytes		M/ uL	Continued		
Hemoglobin	Grams per deciliter	g/ dL	Continued		
Hematocrit	Percentage	%	Continued		
VGM	Femtoliters	fL	Continued		
HCM	picograms	pg	Continued		
CMHbG	Grams per deciliter	g/ dL	Continued		
Leukocytes	Thousands per liter units	Thousands/uL	Continued		
Platelets	Thousands per liter units	Thousands/uL	Continued		
Myelocytes	Percentage	%	Discreet		
Metamyelocytes	Percentage	%	Discreet		
Bands	Percentage	%	Discreet		
Segmented	Percentage	%	Discreet		
Lymphocytes	Percentage	%	Discreet		

Variable	Unit	Symbol	Guy	Measurement method	Normal value
Monocytes	Percentage	%	Discreet		
Eosinophils	Percentage	%	Discreet		
Basophils	Percentage	%	Discreet		
Blastos	Percentage	%	Discreet		
Blood chemistry¹					
Glucose	Milligrams per deciliter	mg/ dL	Continued		
Urea	Milligrams per deciliter	mg/ dL	Continued		
Creatinine	Milligrams per deciliter	mg/ dL	Continued		
Liver function tests¹					
Alanine transferase	Units per liter	U/L	Continued		
Aspartate transferase	Units per liter	U/L	Continued		
Total bilirubin	Milligrams per deciliter	mg/ dL	Continued		
Direct bilirubin	Milligrams per deciliter	mg/ dL	Continued		
Indirect bilirubin	Milligrams per deciliter	mg/ dL	Continued		

¹The measurement method and normal values will be designated by the clinical analysis laboratory designated by the sponsor.

Table 5Scales to be used

The methods and scales that will be used to measure the variables are described below, which are in strict alphabetical order:

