6.2 Eligibility criteria

6.2.1 Inclusion criteria

- Signed informed consent.
- Systemically and ophthalmologically healthy subjects evaluated during the medical history.
- Age between 18 and 45 years.
- Both sexes.
- Blood tests [complete blood count (CBC), three-element blood chemistry (BC), and liver function tests (LFTs)] within normal parameters specified by the reference laboratory with a lower and upper margin of 10%.
- Vital signs are within normal limits. (Resting vital signs: blood pressure \leq 139/89 mmHg , heart rate 60-100 beats per minute, and respiratory rate 12-24 breaths per minute)
- Visual capacity 20/30 or better, in both eyes.
- Intraocular pressure \geq 11 and \leq 21 mmHg .

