6.4.3.1 Visual capacity

Visual acuity (VA) is a test of visual function. Spatial visual acuity is the ability to distinguish separate elements of an object and identify them as a whole. It is quantified as the minimum angle of separation (located at the nodal point of the eye) between two objects that allows them to be perceived as separate objects.

Snellen notation is described as the distance at which the test is performed divided by the distance at which the letter is vertically equivalent to 5 minutes of arc. Thus, at 6 meters, a letter 6/6 (20/20) is equivalent to 5 minutes of arc, a letter 6/12 (20/40) is equivalent to 10 minutes, and a letter 6/60 (20/200) is equivalent to 50 minutes. The Snellen fraction can also be expressed as a decimal (i.e., 20/20 = 1 and 20/40 = 0.5). [43]

VA will be assessed at baseline, without refractive correction, using the Snellen chart. This chart will be placed in a location with adequate natural or artificial lighting and at a distance of 3 m from the subject being assessed. Visual acuity will be measured in each eye, starting with the right eye (RE),

asking the subject to keep both eyes open and using an occluder to cover the left eye (LE); the subject will read aloud the lines indicated by the evaluator. The evaluator will record the smallest line of letters visible as the RE VA in the clinical record. The LE is then assessed using the same method.

The subject's best refractive correction will then be performed, and the examination will be repeated using the obtained refraction. This result will be reported as CV, entered as a fraction in the clinical record and on the Case Report Form (CRF), and will also be entered as a decimal on the CRF. By definition, the CV cannot be less than the VA.

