8.3 Statistical methodology

8.3.1 Analysis of primary and secondary outcome variables

Statistical analysis will be performed by Sophia Laboratories staff . SPSS version 19 (IBM Corporation , Armonk , NY, USA) will be used.

The designated personnel will be blinded to the intervention groups. Coding will be performed using consecutive numbers for each intervention group.

The data will be collected and organized in an Excel spreadsheet. They will then be exported to the SPSS software platform. The variables will be categorized according to their nature.

The results of continuous quantitative variables will be expressed and presented using measures of central tendency and dispersion (mean, standard deviation, and ranges , as appropriate). Nominal and ordinal qualitative variables will be presented using frequencies, proportions, and/or percentages. See **Table 5Scales to be**

Kolmogorov-Smirnov test will be performed to determine whether the distribution is normal in the results obtained in each study group [50].

The statistical analysis of continuous **quantitative variables** to find significant differences (*p*) will be as follows:

- Intra-group analysis : will be determined by the Wilcoxon rank test, for quantitative variables [51]
- Between-group analysis : Kruskal-Wallis test [52]. This nonparametric test is used to determine whether a group of data comes from the same population. Intuitively, it is identical to ANOVA with the data replaced by categories. For quantitative variables, the Student t *statistic is used* .

The level of difference to consider significance will be an alpha of 0.05 or less.

The results of the nominal and ordinal qualitative variables will be presented as frequencies, proportions, and percentages. See Table 1 (section 6.4.3).

Statistical analysis to identify significant differences in **qualitative variables** will be performed by creating 2x2 contingency tables and will be carried out as follows:

- Intra-group difference : McNemar [53]'s test . This test is applied to 2x2 contingency tables with a dichotomous trait, with matched subject pairs, to determine whether the row and column marginal frequencies are equal (marginal homogeneity).
- Difference between groups : Pearson's χ^2 test (or Fisher's exact test).

The level of difference to consider significance will be an alpha of 0.05 or less.

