Eye Comfort Index (ICO) score.	The ICO is a questionnaire designed to measure irritation of the ocular surface, it assesses symptoms	The evaluator will apply the questionnaire to the subject and allow the subject to answer it calmly without any pressure and/or	Discrete quantitative.	
 Score: 0= None, 100 = High discomfort. 	
 - U for Mann-Whitney. - Wilcoxon Ranges.

Chondroitin Sulfate 0.18%/Sodium Hyaluronate 0.2%

	focused on the comfort associated with ocular surface alterations. Elevated values indicate more Severe.	coercion. See ICO Annex.			
Changes in visual capacity (CV)	Visual acuity (VA) is a test of visual function. Spatial VA is the ability to distinguish separate elements of an object and identify them as a whole. It is quantified as the minimum angle of separation (located at the nodal point of the eye) between two objects that allows them to be perceived as separate objects.	Snellen's Primer	Discrete quantitative.	Fraction, normal value = 20/20	
 - U for Mann-Whitney. - Wilcoxon Ranges.
Changes in tear film rupture time (LRT) with fluorescein.	The stability of the tear film is usually evaluated in the clinic by the TRL. It consists of instilling fluorescein on the ocular surface to allow the visualization of the tear film	It will be measured at the end of a blink and will be asked not to blink immediately until the tear film on the cornea is broken.	Continuous quantitative.	> 10 seconds.	
 - U for Mann-Whitney. - Wilcoxon Ranges.

Chondroitin Sulfate 0.18%/Sodium Hyaluronate 0.2%

	and measure the time it takes to break since the last blink.				
Changes in corneal and conjunctival staining with lysmine green.	Detection of epithelial defects in the conjunctiva and cornea.	Direct observation with slit lamp, Oxford scale graduation. See annex Oxford scale.	Ordinal Qualitative	
Degrees:
 
The staining is presented by a series of panels (A-E). Stain points range from 0-5 for each panel and 0-15 for the total exposed area of the conjunctiva and cornea.
	
 - Pearson's square chi or Fisher's exact. - McNemar test (if applicable).

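### Visual capacity is nominal in the protocol, sent to 2x2 tables with no stated cut, but a quantitative change tested by ranks in the SAP

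*Protocol*

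**What the plan says.** **Protocol.** The Table 5 row in section 6.4.3 reads "Visual capacity Fraction Snellen Nominal Primer 20/20", that is, type nominal with normal value 20/20. Section 8.3.1 says that the analysis of qualitative variables, nominal and ordinal, "will be performed by creating 2x2 contingency tables and will be carried out as follows": McNemar within group and, between groups, "Pearson's χ^2 test (or Fisher's exact test"). No dichotomy is defined for visual capacity.

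Other parts of the protocol treat vision as a measured change. Section 5.5.3 sets the objective as safety through changes in visual ability. Section 6.4.3.1 has the best-corrected value recorded as a fraction and adds that it "will also be entered as a decimal on the CRF". The entry criterion in 6.2.1 is "Visual capacity 20/30 or better, in both eyes", so eyes at 20/25 and 20/30 can be enrolled.

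**SAP.** Table 2 names the variable as changes in visual capacity, types it as discrete quantitative, and assigns Mann-Whitney U and Wilcoxon. Its normal-value cell is "Fraction, normal value = 20/20", the same value as in the protocol. The SAP's title page cites protocol version 2.0; the protocol supplied is version 4.0. SAP Table 3 also appears to carry a 2x2 code in the visual ability row, but its columns are broken in the text available.

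**The concern.** Visual capacity is a listed secondary safety outcome with its own objective. An analyst who follows the protocol builds a 2x2 table and must choose the cut. One who follows the SAP ranks the changes. Neither document says which prevails.

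The nominal label is also wrong in itself, because Snellen fractions are ordered and the CRF holds a number. The practical risk lies in the missing cut. The only values an analyst can find are the normal value of 20/20 and the entry limit of 20/30, and a split of final status at either one discards change:

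- At 20/20, an eye that enters at 20/25 or 20/30 is already on the abnormal side, so further loss cannot register.
- At 20/30, a fall from 20/20 to 20/25 or to 20/30 does not register.

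**Working it through.** The plan gives no power or effect size for visual capacity, so there is no stated figure to reproduce. The check asks how much the choice of analysis could matter.

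**Inputs from the documents.** 16 subjects (16 eyes) per arm (protocol 6.6); alpha 0.05 (8.3.1), taken as two-sided; candidate cuts 20/20 (Table 5) and 20/30 (6.2.1).

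**Assumptions not in the documents.** A share q of eyes starts at exactly 20/20 and the rest at 20/25 or 20/30. A one-line loss occurs in r = 50% of PRO-165 and 5% of comparator eyes. There is no test-retest noise.

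**Step 1: final status split at 20/20.** The proportion worse than 20/20 at the final visit is (1 − q) + q·r:

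- q = 0.6: 0.4 + 0.6 × 0.50 = 0.70 v 0.4 + 0.6 × 0.05 = 0.43
- q = 0.8: 0.2 + 0.8 × 0.50 = 0.60 v 0.2 + 0.8 × 0.05 = 0.24
- q = 0.9: 0.1 + 0.9 × 0.50 = 0.55 v 0.1 + 0.9 × 0.05 = 0.145
- q = 1: 0.50 v 0.05

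Eyes that start below 20/20 add the same background to both arms and shrink the contrast. The share of one-line losses that cross the cut is simply q.

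**Step 2: power.** The counts a and b are binomial, so power = Σ Bin(a; 16, p1) × Bin(b; 16, p2) over all tables with p ≤ 0.05. For a one-line, noise-free loss the change is 0 or 1, so asymptotic Mann-Whitney on change can be enumerated in the same way.

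| Analysis | Fisher | Chi-square | Mann-Whitney |
|---|---|---|---|
| Change in lines, any q | – | – | 0.87 |
| Final status at 20/20, q = 0.6 | 0.21 | 0.35 | – |
| Final status at 20/20, q = 0.8 | 0.40 | 0.56 | – |
| Final status at 20/20, q = 0.9 | 0.54 | 0.72 | – |
| Final status at 20/20, q = 1 | 0.78 | 0.90 | – |
| Worsened / not worsened, any q | 0.78 | 0.90 | – |

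Simulations of the same settings agree to within about 0.03. With q = 0.6 they gave 0.21 to 0.24 for Fisher and 0.38 for chi-square; Mann-Whitney on change was 0.86 to 0.88.

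**Step 3: final status split at 20/30.** Only eyes that start at 20/30 can cross. If 15% do, the proportions are 0.15 × 0.50 = 0.075 v 0.15 × 0.05 = 0.0075, and Fisher's power is below 1%.

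**Step 4: smaller effects.** Mann-Whitney on change has power of about 0.47 at 30% v 5% (simulations 0.46 to 0.50) and about 0.21 at 20% v 5%. With 40% losing one line v none, but 10% random one-line noise each way, simulation gives about 0.49.

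**The case against.** The strongest reply is that a 20/20 split is nowhere prescribed. The normal-value column is a reference column, filled in for intraocular pressure and break-up time too, and the SAP gives the same 20/20. A worsened/not-worsened table fits both section 8.3.1 and the objective of change. It has 0.90 power by chi-square and 0.78 by Fisher, against 0.87 for Mann-Whitney. This stands: the power loss comes from dichotomising final status, not from the nominal label alone.

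A reader might infer that the protocol's analysis would miss most loss of vision and that the SAP's would usually detect it. The documents support neither half.

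- **Missing most loss.** Low power between arms is not the same as missed losses. With 60% to 90% of eyes at 20/20, 60% to 90% of one-line losses cross the cut. Most would fail to cross only if fewer than about half of eyes started exactly at 20/20. No baseline distribution is given, and these are best-corrected healthy adults aged 18 to 45.
- **Usually detecting it.** The 0.87 assumes a large, noise-free effect that the documents do not support; Step 4 shows how quickly it falls.

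Losses also have other ways to surface. Section 8.3.1 requires frequencies and percentages, and 6.4.3.4 requires pathological findings to be reported under the adverse-event rules. Finally, the safe-and-tolerable rule in both documents uses primary outcomes only. All of this limits the size of the point. None of it reconciles the two classifications or supplies the missing cut.

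**Conclusion.** The contradiction is certain: two variable types and two sets of tests for one secondary safety outcome, a SAP tied to an older protocol version, and a nominal label at odds with the protocol's own objective and data collection.

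Its consequence is conditional. If final status is split at the inferred 20/20 cut, power falls from about 0.87 to 0.21–0.54 (Fisher) or 0.35–0.72 (chi-square) as the share of eyes starting at 20/20 runs from 60% to 90%. If all eyes start at 20/20, or the table is worsened/not worsened, chi-square loses nothing and Fisher about 0.09 (0.87 − 0.78). These figures rest on an assumed one-line loss in 50% v 5% without noise and on an assumed baseline mix. The point is minor to moderate and does not alter the primary conclusion rule.

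**What to change.** 1. In protocol Table 5, reclassify visual capacity as quantitative and take it out of the 2x2 analyses of final status. Relabelling it ordinal would not be enough, because 8.3.1 sends ordinal variables to 2x2 tables as well.
2. In both documents, define the endpoint as change from baseline in the treated right eye, from the decimal already on the CRF, expressed in lines or logMAR.
3. Use the SAP's Mann-Whitney between arms and Wilcoxon within arm. Section 8.3.1 needs a matching edit: it names Kruskal-Wallis and Student t between groups and refers to continuous quantitative variables, whereas the SAP calls this one discrete.
4. Report by arm the number of subjects losing one line, and two or more lines.
5. Update the SAP to cite and match protocol 4.0, and check the visual ability row of SAP Table 3.

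The cost is one table cell, a short edit to 8.3.1, and the SAP row with its version reference. No new data are needed, and the conversion to lines or logMAR is a single derived variable.

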6.4.3.1 Visual capacity

Visual acuity (VA) is a test of visual function. Spatial visual acuity is the ability to distinguish separate elements of an object and identify them as a whole. It is quantified as the minimum angle of separation (located at the nodal point of the eye) between two objects that allows them to be perceived as separate objects.

Snellen notation is described as the distance at which the test is performed divided by the distance at which the letter is vertically equivalent to 5 minutes of arc. Thus, at 6 meters, a letter 6/6 (20/20) is equivalent to 5 minutes of arc, a letter 6/12 (20/40) is equivalent to 10 minutes, and a letter 6/60 (20/200) is equivalent to 50 minutes. The Snellen fraction can also be expressed as a decimal (i.e., 20/20 = 1 and 20/40 = 0.5). [43]

VA will be assessed at baseline, without refractive correction, using the Snellen chart. This chart will be placed in a location with adequate natural or artificial lighting and at a distance of 3 m from the subject being assessed. Visual acuity will be measured in each eye, starting with the right eye (RE),

asking the subject to keep both eyes open and using an occluder to cover the left eye (LE); the subject will read aloud the lines indicated by the evaluator. The evaluator will record the smallest line of letters visible as the RE VA in the clinical record. The LE is then assessed using the same method.

The subject's best refractive correction will then be performed, and the examination will be repeated using the obtained refraction. This result will be reported as CV, entered as a fraction in the clinical record and on the Case Report Form (CRF), and will also be entered as a decimal on the CRF. By definition, the CV cannot be less than the VA.

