5.5.3 Secondary Objectives

- To describe the safety of PRO-165 ophthalmic gel through changes in intraocular pressure.
- To describe the safety of PRO-165 ophthalmic gel through changes in visual ability.
- To describe the safety of PRO-165 ophthalmic gel through changes in laboratory testing.
- To describe the safety of PRO-165 ophthalmic gel when evaluating ocular surface stains
- To describe the safety of PRO-165 ophthalmic gel through changes in tear break-up time.
- To describe the safety of PRO-165 ophthalmic gel through changes in vital signs.
- To describe the tolerability of PRO-165 ophthalmic gel by the presence of the symptoms: burning, foreign body sensation, and itching.

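### Change in visual capacity is tested with no stated transformation and, as most naturally read, as a difference of Snellen decimals, which weights the same loss by starting acuity and costs some within-arm power; logMAR would avoid this (minor)

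*Protocol*

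**What the plan says.** Protocol 6.4.3.1 describes acuity by an angle: "It is quantified as the minimum angle of separation". Readings are by whole chart lines ("The evaluator will record the smallest line of letters visible"). The best-corrected result goes into the clinical record and the CRF as a fraction "and will also be entered as a decimal on the CRF". The section gives the conversion as 1 for 20/20 and 0.5 for 20/40. The chart's lines are not listed.

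Entry requires "Visual capacity 20/30 or better, in both eyes" (protocol 6.2.1), with no upper limit. One secondary objective is "To describe the safety of PRO-165 ophthalmic gel through changes in visual ability" (protocol 5.5.3).

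SAP Table 2 lists change in visual capacity as discrete quantitative, gives its scale as "Fraction, normal value = 20/20", and assigns Mann-Whitney and Wilcoxon tests. Protocol Table 5 (6.4.3) types the same variable as nominal. Neither document mentions logMAR, a count of lines or any other transformation.

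**The concern.** A fraction used as a number is its decimal, and the decimal is the reciprocal of the angle by which the protocol defines acuity. Differences of reciprocals do not keep vision changes in order of size, because the same proportional loss shrinks as starting acuity gets worse.

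Rank tests do not cure this. Ranks of raw values survive any monotone transformation, but ranks of differences do not. Eligible eyes start anywhere from 20/30 upwards, so unequal weighting can arise within one arm. At stake is how well the within-arm test of a safety variable detects vision loss, and whether the mean and SD of the change are meaningful.

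**Working it through.** **Inputs.** From the documents: the decimal conversion, whole-line reading, entry at 20/30 or better, 16 eyes per arm and alpha 0.05. Assumed, because the documents do not give them: the chart lines, baseline mix, retest noise and true loss.

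**1. The protocol's own figures.** Decimal = 20/denominator gives 20/20 = 1.0 and 20/40 = 0.5, as stated.

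**2. The two scales.** Protocol 6.4.3.1 doubles the letter's angle from 20/20 to 20/40, so the relative angle is denominator/20 and the decimal is its reciprocal. With logMAR = log10(denominator/20), the change is log10(final denominator/baseline denominator), which depends only on the ratio.

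**3. Same proportional loss, different decimal change.** This holds on any chart that shows these lines.

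| Change | Decimal | logMAR (loss +) |
|---|---|---|
| 20/20 to 20/40 | 0.500 − 1.000 = −0.500 | log10(2) = 0.301 |
| 20/30 to 20/60 | 0.333 − 0.667 = −0.333 | log10(2) = 0.301 |
| 20/15 to 20/20 | 1.000 − 1.333 = −0.333 | log10(4/3) = 0.125 |
| 20/30 to 20/40 | 0.500 − 0.667 = −0.167 | log10(4/3) = 0.125 |

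**4. A gain outranking a larger loss.** Assumed lines: 20/10, 15, 20, 25, 30, 40, 50.

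| Change | Decimal | Size in logMAR |
|---|---|---|
| One-line gain, 20/20 to 20/15 | +0.333 | 0.125 |
| Two-line loss, 20/25 to 20/40 | −0.300 | 0.204 |
| Two-line loss, 20/30 to 20/50 | −0.267 | 0.222 |

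The signed-rank test ranks absolute changes, so on decimals the gain ranks above both losses. On logMAR the order is reversed. Other assumed charts:
- With no 20/25 line, 20/20 to 20/15 (+0.333) still exceeds 20/30 to 20/50 (−0.267).
- On a geometric chart, 20/20 to 20/16 (+0.250) exceeds 20/32 to 20/50 (−0.225).
- On a chart ending at 20/20, the largest one-line gain is +0.200 and the smallest two-line loss is −0.267. There is no inversion.

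**5. Effect on the signed-rank sums.** Take 16 eyes: 8 unchanged, 4 going from 20/20 to 20/15, and 4 from 20/25 to 20/40.
- Decimal: the losses (0.300) share ranks 1–4, sum 10, and the gains (0.333) share ranks 5–8, sum 26. W+ = 26, W− = 10, a net gain.
- logMAR: the gains (0.125) sum to 10 and the losses (0.204) to 26. W+ = 10, W− = 26, a net loss.

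This example was built to show the mechanism. It is not a forecast.

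**6. Mann-Whitney.** On visit values the result is the same on either scale (p = 0.657 both ways in a test set). On signed change every gain still ranks above every loss, but the order among losses and among gains can be wrong: the one-line loss 20/15 to 20/20 (−0.333) counts as worse than the two-line loss 20/25 to 20/40 (−0.300).

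**7. Power.** Simulated trials had 16 eyes per arm and two-sided alpha 0.05, with 800 or 1,000 trials per setting. Assumed settings included baselines from 20/15 to 20/30, one-line retest noise in 30–50% of eyes, and a true loss of one line in 40% or two lines in 25–40% of PRO-165 eyes. The change in power when logMAR replaces the decimal:

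| Test and chart | Percentage points |
|---|---|
| Within-arm Wilcoxon, chart to 20/10 | about 2 to 24 |
| Within-arm Wilcoxon, chart to 20/15 | about 1 to 18 |
| Within-arm Wilcoxon, chart to 20/20 | about −2 to +6 |
| Between-arm Mann-Whitney | about −2 to +7 |

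The simulation standard error of a single power near 50% is √(0.25/1,000) = 1.6 points, or √(0.25/800) = 1.8 points, so the range ends near zero cannot be told from no difference. With no true change and no chart ceiling, rejection was about 3–6% on both scales.

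**The case against.** **The decimal scale is inferred.** No sentence says that a decimal difference is analysed. The SAP names the fraction. Protocol Table 5 says nominal, and protocol 8.3.1 sends nominal variables to frequencies, McNemar and chi-square or Fisher tests, where the decimal plays no part. The SAP's general between-group rule also does not say whether Mann-Whitney uses the change or the visit value. All of this stands as a caveat. But the Table 2 row is about change, assigns rank tests for quantities and specifies no other number, so the decimal difference remains the natural reading.

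**The inversion is conditional.** A reader might infer that chance gains will generally outrank real losses. The documents do not support that. The inversion needs lines better than 20/20 and affects only the within-arm signed-rank test. Some asymmetry is also in the chart itself: 20/20 to 20/15 exceeds 20/20 to 20/25 on logMAR too (0.125 against 0.097).

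**No bias towards improvement under no change.** A reader might infer a false signal of benefit. The rejection rates are about the same on both scales, so what remains is lower power when vision is truly lost.

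**The consequence is limited.** The hypotheses compare arms, and there the difference is small. The safe-and-tolerable rule (protocol 8.3.1; SAP Methods of Analysis) uses only the primary variables. Protocol 6.4.3.4 requires a complete eye examination with pathological changes reported as adverse events. It would therefore be wrong to conclude that the trial would miss vision loss; the weakness is in one secondary analysis.

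**Conclusion.** The point holds as a minor one. Read in the most natural way, the SAP tests a difference of Snellen decimals, and on that scale equal proportional losses count unequally whatever the chart. The larger effect, a one-line gain ranking above a two-line loss, holds only for the within-arm signed-rank test and only if the chart reads better than 20/20.

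The practical cost is within-arm power to detect vision loss: up to about 24 points under the most favourable assumptions, and about nothing on a chart ending at 20/20. These figures rest on assumed chart lines, baseline mix, retest noise and true loss, so they show a plausible range and are not an estimate for this trial. The sample size and the primary safe-and-tolerable rule are unaffected.

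**What to change.** - In SAP Table 2 (visual capacity row) and protocol 6.4.3.1, derive logMAR = log10(denominator/numerator) from the fraction already on the CRF.
- State that the change in logMAR is used for the Wilcoxon test, the Mann-Whitney test and the mean and SD. Keep the fraction for display.
- In protocol Table 5, replace the nominal type for visual capacity with one that matches the SAP's quantitative analysis, so that a single analysis rule applies.

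The cost is one derived variable, a sentence in each document and one table entry. It needs no new data, visits, procedures or subjects.
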